- h) During treatment period, at end of treatment visit. The patient should be contacted by a nurse 30 days after the last dose of study treatment (or at the time of initiation of subsequent treatment if started before 30 days) to check if the patient has experienced any late adverse events. Grade 3 or higher adverse events at least possibly related to study treatment and deaths due to any cause should be reported as a late adverse event on the Survival and Disease Status Follow-Up/Event Monitoring form if they were not already reported on the Adverse Event form for the last cycle and they occurred prior to any subsequent treatment and 30 days post-end of treatment
- i) For females of childbearing potential, a negative pregnancy test (urine or serum) must be documented within 14 days of starting treatment on the study and for patients starting Cycle 4 (daratumumab+lenalidomide) in accordance with the REVLIMID REMSTM program. A female of childbearing potential (FCBP) is a sexually mature female who: 1) has not undergone a hysterectomy or bilateral oophorectomy; or 2) has not been naturally postmenopausal for at least 24 consecutive months (i.e., has had menses at any time in the preceding 24 consecutive months).
- j) Patients starting Cycle 4 treatment (daratumumab+lenalidomide) prior to starting treatment with REVLIMID
- k) To be collected at the end of every cycle of maintenance therapy while the patient is receiving lenalidomide
- l) UPEP testing required at baseline only. Subsequent testing will be as needed per physician discretion.

\*Repeat Electrophoresis of serum and urine, Serum immunoglobulins, Immunofixation serum and urine, and Immunoglobulin free light chain only if the assessments were not completed 14 days prior to End of Treatment visit.

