## 11.0 Treatment Evaluation - The International Myeloma Working Group (IMWG) uniform response criteria (Kumar et al, 2016) will be used to assess response to therapy

### 11.1 Terms and definitions

- **M-protein:** synonyms include M-spike, monoclonal protein and myeloma protein, paraprotein, M-component.

Serum M-protein level is quantitated using densitometry on SPEP except in cases where the SPEP is felt to be unreliable.

- M-proteins migrating in the β-region (usually IgA M-proteins)
- Cases in which the M-protein is so large and narrow on agarose (some specimens >4 g/dL) that they underestimate the actual immunoglobulin level (by greater than 1500 mg/dL) due to technical staining properties of the agarose gel.
- Cases in which there are multiple peaks of same M-protein (aggregates or dimers)

If SPEP is not available or felt to be unreliable (above examples) for routine M-protein quantitation, then quantitative immunoglobulin levels derived from nephelometry or turbidometry can be accepted, with the exception that quantitative IgG may not be used. However, this must be explicitly reported at baseline, and only nephelometry can be used for that patient to assess response. SPEP derived M-protein values and quantitative nephelometric immunoglobulin values cannot be used interchangeably.

Urine M-protein measurement is estimated using 24-h UPEP only. Random or 24 h urine tests measuring kappa and lambda light chain levels are not

reliable and are not recommended.

**FLC estimation** is currently carried out using the serum FLC assay (Freelite, The Binding Site Limited, UK). Patients with kappa/lambda FLC ratio  $<0.26$  are defined as having monoclonal lambda FLC and those with ratios  $>1.65$  as having a monoclonal kappa FLC. The monoclonal light chain isotype is considered the involved FLC isotype, and the opposite light chain type as the uninvolved FLC type.

- **Response terms:** The following response terms will be used: stringent Complete Response (sCR), complete response (CR), very good partial response (VGPR), partial response (PR), Minimal Response (MR), stable disease (SD), and progressive disease (PD).

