## 11.2 Clarification of test indications

Listed below are the minimal required tests required to assess response based on the characteristics of their disease at on study.

Table 11.2				
Tests Required To Assess Response (Must Be Done At Each Disease Measurement Visit except as indicated  )				
On Study Baseline Value	SPEP 	24 hr UPEP 	Ig FLC	BM Bx
Serum M-protein $\geq$ 1 g/dl, and urine M-protein $\geq$ 200 mg/24 hrs	X	X		
Serum M-protein $\geq$ 1 g/dl, but urine M-protein < 200 mg/24 hrs	X			
Serum M-protein <1 g/dl, and urine M-protein $\geq$ 200 mg/24 hrs		X		
Serum M-protein < 1 g/dl, urine M-protein < 200 mg/24 hrs, but involved Ig FLC is $\geq$ 10 mg/dL			X	
Serum M-protein < 1 g/dl, urine M-protein < 200 mg/24 hrs, involved Ig FLC is <10 mg/dL, bone marrow $\geq$ 30% plasma cells				X 

 ***SPEP, UPEP, Immunofixation studies of both serum and urine, and Bone marrow biopsy*** are required to document CR regardless of registration values, and in addition ***FLC measurement and bone marrow immunophenotyping*** is required to document sCR. SPEP and UPEP are required to document VGPR regardless of registration values.

 For serum measurable patients, 24 hour urine does not need to be confirmed (i.e. repeated after documented response) for any response category

 At a minimum, a bone marrow biopsy should be repeated every 3 months until documented response. Bone marrow biopsy results do not need to be repeated after documented response.

 If serum M-protein is being followed by quantitative immunoglobulin levels derived from nephelometry or turbidometry, quantitative immunoglobulins are required. SPEP is only required to document CR or VGPR.

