### 11.3 Confirmed response

In order to be classified as a hematologic response, confirmation of serum M-protein, serum immunoglobulin free light chain (when primary determinant of response) and urine M- protein (when primary determinant of response) results must be made by verification on two consecutive determinations.

- Bone marrow aspirate and biopsy are **only** required to document CR or sCR, except for patients with evaluable disease **only**, where a bone marrow is required to document all response categories including progression. However, a second confirmatory bone marrow is **not** required to confirm response in any case.
- Radiographic studies are not required to satisfy these response requirements; however, if radiographic studies were performed there should be no evidence of progressive or new bone lesions.

Appropriate tests required to document and confirm response are listed in Table 11.2

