### 11.5 Response and Progression

Criteria for response and progression are listed in Table 11.5. Progressive disease for all patients as defined in Table 11.5.

Baseline values for disease assessment: All disease response measurements will be based on the values obtained at the time of diagnosis if there has been no relapse prior to transplant. If patients had a disease relapse prior to transplant, the baseline values will be those obtained at the time of relapse immediately prior to the transplant. If patient had treatment for the relapsed disease prior to transplant, the values will be from prior to this therapy, ie, the time of relapse.

Table 11.5

IMWG MRD NEGATIVITY CATEGORY	RESPONSE CRITERIA a
Flow MRD k	Absence of phenotypically aberrant clonal plasma cells by MPF on bone marrow aspirates using the EuroFlow standard operation procedure for MRD detection in multiple myeloma (or validated equivalent method) with a minimum sensitivity of 1 in $10^5$ nucleated cells or higher
Imaging + MRD-negative	MRD negative as defined by MPF or NGS PLUS Disappearance of every area of increased tracer uptake found at baseline or a preceding PET/CT or decrease to < mediastinal blood pool Standard uptake value or decrease to less than that of surrounding normal tissue
STANDARD IMWG RESPONSE CATEGORY	RESPONSE CRITERIA a
Stringent Complete Response (sCR) b	CR as defined plus Normal FLC ratio and • Absence of clonal PCs by immunohistochemistry or 2- to 4-color flow cytometry i
Complete Response (CR) b	• Negative immunofixation of serum and urine c and • Disappearance of any soft tissue plasmacytoma and • <5% PCs in Bone Marrow and • If the only measurable disease is FLC, a normal FLC ratio d
Very Good Partial Response (VGPR)	• Serum and urine M-protein detectable by immunofixation but not on electrophoresis c or • $\geq 90\%$ reduction in serum M-protein and urine M-protein <100 mg/24 h c • If the only measurable disease is FLC, a $>90\%$ reduction in the difference between involved and uninvolved FLC levels

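### Test schedule note l makes UPEP discretionary after baseline while Table 11.2 makes it mandatory for urine-measurable patients; neither is ranked, and the response baselines conflict

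*Combined protocol and SAP*

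**What the plan says.** **Testing rule**

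- Section 4.1, note l: "UPEP testing required at baseline only. Subsequent testing will be as needed per physician discretion". The note sits on the SPEP/UPEP cells for Cycle 2 (to 4) Day 1, pre-ASCT, Day 100 and the end of each maintenance cycle. The End of Treatment cell has an asterisk instead: serum and urine electrophoresis is repeated there unless done in the previous 14 days.
- Table 11.2 lists minimum tests under the words "Must Be Done At Each Disease Measurement Visit except as indicated" and marks 24-hour UPEP in both rows with urine M-protein of at least 200 mg/24 h.
- Table 11.2, footnote 1: "SPEP and UPEP are required to document VGPR regardless of registration values". It also lists UPEP among the tests needed for CR.
- Table 11.2, footnote 2: "For serum measurable patients, 24 hour urine does not need to be confirmed". A bracket explains this as a repeat once response is documented.
- Section 11.1: "Urine M-protein measurement is estimated using 24-h UPEP only".
- Section 11.3: where urine M-protein is the primary determinant of response, confirmation of "results must be made by verification on two consecutive determinations".

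**Baseline**

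- Table 11.2 selects tests by "On Study Baseline Value".
- Section 11.5: "All disease response measurements will be based on the values obtained at the time of diagnosis" if there was no relapse before transplant, and otherwise on the relapse values.
- Section 16.42 compares response with values at registration.
- Section 12.5 refers to the time given in a section 3.18. The inclusion list ends at 3.17, which carries the diagnosis/relapse rule.

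**The concern.** A site that works from the test schedule can satisfy note l and breach Table 11.2 at the same visit. The overall response rate (ORR) is the objective status at the Day 100 assessment. In Table 11.5, partial response has a urine component when urine M-protein was present at baseline. Progression on urine is a 25% rise from the lowest value, with an absolute rise of at least 200 mg/24 h. Both need quantitative urine values during treatment, and a 24-hour collection not made at Day 100 cannot be recovered later.

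The baseline conflict compounds this. Patients enter after induction, so a patient who was urine-measurable at diagnosis may be below 200 mg/24 h at registration. Which baseline applies decides whether that patient falls under the mandatory UPEP rows at all, and also what the ORR is measured against.

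**Working it through.** No stated figure in the plan rests on this point, so there is none to reproduce. The check sets the rules side by side, then does the calendar arithmetic.

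**1. Who is affected**

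| Baseline M-protein | Note l after baseline | Table 11.2 | If no UPEP is done at Day 100 |
|---|---|---|---|
| Urine ≥200 mg/24 h, serum <1 g/dL | Discretionary | UPEP is the only listed test, every visit | Response cannot be documented; urine progression cannot be seen |
| Both measurable | Discretionary | SPEP and UPEP, every visit; footnote 2 waives the confirmatory repeat | Urine part of PR missing; progression visible through serum only |
| Serum ≥1 g/dL only | Discretionary | SPEP; UPEP to document VGPR or CR | PR can be shown on SPEP and counts towards ORR; only depth of response is affected |

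**2. Whether another scheduled test fills the gap**

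Urine immunofixation is scheduled at the same visits without note l, but it does not quantify M-protein. Section 11.1 accepts only 24-hour UPEP for that. It also tells sites to ignore FLC, except for sCR, unless FLC alone qualified the patient.

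**3. Age of the last assured UPEP at Day 100, if note l governs**

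Inputs:
- baseline test up to 14 days before registration (Section 4.1);
- treatment start up to 28 days after registration (Section 6.15);
- consolidation cycles of 28 days, the last running 28 to 84 days up to transplant (Section 7.11);
- Day 100 visit 90 to 110 days after transplant (Section 7.12).

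The minimum puts the test, registration and Cycle 1 Day 1 on one day, with transplant straight after the last consolidation cycle. Dose delays and the 3-day visit window are ignored.

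- Two cycles, minimum: 28 + 28 + 90 = 146 days.
- Two cycles, maximum: 14 + 28 + 28 + 84 + 110 = 264 days.
- Four cycles, minimum: (3 × 28) + 28 + 90 = 202 days.
- Four cycles, maximum: 14 + 28 + (3 × 28) + 84 + 110 = 320 days.

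**4. Visits at which UPEP is discretionary under note l, through one year of maintenance**

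- Two cycles: 1 (Cycle 2 Day 1) + 1 (pre-ASCT) + 1 (Day 100) + 12 (maintenance) = 15, of which 3 fall up to and including Day 100.
- Four cycles: 3 + 1 + 1 + 12 = 17, of which 5 fall up to and including Day 100.

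These are visits without an assured test, not tests that will be missed.

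**5. Effect on ORR**

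Section 16.42 divides responders at Day 100 by all evaluable patients. A responder whose status cannot be determined therefore stays in the denominator and, on the assumption of being counted as a non-responder, leaves the numerator. With 45 evaluable patients each such patient costs 1/45 = 2.2 percentage points.

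The documents do not give the urine-measurable share. For scale only, assume a share of 10% to 40%, half of these without UPEP, and all of that half true responders:
- 45 × 0.10 × 0.5 = 2.25, about 2 patients, 2/45 = 4.4 points;
- 45 × 0.40 × 0.5 = 9 patients, 9/45 = 20.0 points.

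**6. Baselines**

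Section 11.2 uses on-study values, Section 11.5 diagnosis or relapse values, Section 16.42 registration values, and Section 12.5 a section that is absent. Section 12.1 expects entrants in CR or sCR. Read on study, such a patient may fit none of the five rows of Table 11.2, whereas the diagnosis or relapse value places the same patient in a row.

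**The case against.** The best defence is that the discretion in note l sits on top of the Section 11.2 minimum, so that as-needed testing already includes whatever Table 11.2 demands. That works for footnote 1, where documenting VGPR or CR is a natural trigger. It does not work for the every-visit requirement in the urine rows: note l has no cross-reference and gives the choice to the physician.

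The affected group can also be argued down. Footnote 2 could be read as releasing patients measurable in both serum and urine from any further UPEP after a documented response. Its wording concerns confirmation, so the narrower reading is the better one, but the bracket leaves room for doubt. Separately, a patient who enters in VGPR or better by Table 11.5 has urine M-protein below 100 mg/24 h or none on electrophoresis, and so cannot be in an on-study urine row. That is right on the on-study baseline and fails on the diagnosis or relapse baseline, which is why the baseline has to be settled.

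Three stronger readings are tempting and are not supported:

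- A reader might infer that there are no urine data during treatment. Immunofixation remains scheduled, and End of Treatment electrophoresis is outside note l. Only the quantitative UPEP between registration and End of Treatment is unassured.
- A reader might infer that UPEP will certainly be absent at all 15 or 17 visits. The lack of assurance holds only if note l overrides Table 11.2. If Table 11.2 governs, urine-measurable patients are tested at their disease measurement visits.
- A reader might infer that the plan is silent on the baseline. It is not: several sections name one, and they disagree.

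**Conclusion.** The contradiction is real and should be corrected. Note l and Table 11.2 give opposite instructions for urine-measurable patients, and no section ranks them. If note l is followed, Day 100 response and urine-based progression are not assured, mainly in patients measurable by urine only and, for PR and PD, in those measurable in both serum and urine. The last assured quantitative value would be 146 to 264 days old (202 to 320 with optional cycles) and would predate the first daratumumab dose. The conflicting baselines are a second defect, affecting both who counts as urine-measurable and what the ORR means.

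The consequence is limited. ORR and progression-free survival (PFS) are secondary and descriptive, with no decision rule. PFS still captures death and progression shown by serum, bone or plasmacytoma. The total effect on ORR cannot be sized, because the urine-measurable share is not stated; the 4.4 to 20.0 point range is an assumption and not an estimate.

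A reader might also infer that the primary endpoint is compromised. Sections 16.11 and 16.411 define it by marrow flow cytometry at Day 100 with no CR condition. UPEP would reach it only if Table 11.5 footnote k, which makes CR a condition of flow MRD negativity, is applied.

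**What to change.** - Amend note l so that UPEP is discretionary except where Table 11.2 requires it. State those cases: each disease measurement visit, including Day 100, for patients followed by urine M-protein; and, for any patient, the visit at which VGPR, CR or sCR is first documented.
- Keep footnote 2 as a waiver of the confirmatory repeat only, in serum-measurable patients, and say that it does not remove the Day 100 test in patients followed by urine.
- Name one response baseline and use it in Sections 11.2, 11.5, 12.5 and 16.42. Correct the 3.18 reference to 3.17. Sections 3.17 and 11.5 already share the diagnosis/relapse rule, and the corrected Section 12.5 would join them, so leaving on-study or registration values in 11.2 or 16.42 would keep the conflict alive.

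The text change is short. The running cost is more 24-hour urine collections than note l implies, and somewhat more than a literal on-study reading of Table 11.2 if the diagnosis or relapse baseline is chosen. Section 19.1 charges routine care to patients and Section 19.2 funds no tests from research, so patients bear that cost.

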#### 4.2 Event Monitoring/Survival Follow-up

	Event Monitoring Phase 				
	Q 3 months until PD or subsequent treatment	At PD or subsequent therapy	After PD or subsequent therapy Q 6 months	Death	New Primary
Event Monitoring	X	X	X	X	At each occurrence

1. If a patient is still alive 3 years after registration, no further follow-up is required

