### 1.4 Role of ASCT and Post-ASCT Maintenance Therapy in Multiple Myeloma

ASCT is the standard of care in transplant-eligible MM patients based on several phase III trials and meta-analyses depicting significant improvement in progression free Survival (PFS), CR, and OS. Attal et al in IFM-90 trial reported superior outcomes of high-dose chemotherapy (HDC) followed by ASCT compared to conventional chemotherapy alone, with improved OS (57%), CR (22%) and event-free survival (EFS) (16%), and median OS 57 months versus 44 months. The majority of post-ASCT patients relapse with median PFS around 36 months. Relapses are harder to treat and prognosis gets worse with each relapse. Multiple studies have suggested a survival advantage from attaining a deeper response to induction chemotherapy and ASCT, and sustained CR was shown to be a surrogate for OS in MM population. The clinical significance of MRD negativity using highly sensitive methods has been reviewed and goal of MRD is to stratify the risk and evaluate the response to novel agents. Despite remarkable improvement in treatment outcome in MM with the use of IMiDs and novel agents, it remains an incurable disease. Multiple studies in the last few years have examined the role of consolidation and/or maintenance to eliminate MRD after HDC-ASCT in MM. Post-ASCT consolidation and/or maintenance strategies have been studied in multiple trials including single and combination agents including interferon-alpha,

glucocorticoids, thalidomide, lenalidomide, bortezomib and combination regimens to determine compare PFS and OS to improve long term outcomes.

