#### 7.13 Maintenance (Cycles 4 and Beyond, or cycle 6 and beyond as the case may be for that patient)

- All patients will be initiated on maintenance therapy as below within 14 days of completing Day 100 visit post-SCT.

Agent	Dose	Route	Day	Cycles
Daratumumab	16 mg/Kg* (IV) 1,800 mg (Injection)	IV or Injection	1	Cycle 4-15 (or 6-17)
Lenalidomide	10 mg*	PO	1-21	Cycle 4-15

				(or 6-17)
--	--	--	--	-----------

Cycles 4-15 (or 6-17) length = 28 days

\*Any dose-adjustments will be made as per the prescriber information.

Daratumumab administrations as per prescriber information and institutional guidelines.

Note: Thromboprophylaxis is required as standard of care (see Section 9.3) for all patients on maintenance treatment.

- **NOTE:** Prior to Cycle 16 (or 18), patients who are still maintaining response will proceed to maintenance with single-agent daratumumab every 3 months till disease progression or unwanted adverse events, if any. Cycles 16 and beyond length = 90 days (3 months).
- In the event of disease progression, intolerable adverse event or patient refusal for continued therapy, they will proceed to event monitoring without any additional anti-MM therapy.
- Considering that there are newer immunotherapy compounds being made available for the treatment of multiple myeloma, based on the initial results of this clinical trial, amendments may be put in place to add more arms to the study with newer, proven safe combination regimens, especially for maintenance treatment.

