## 13.0 Treatment/Follow-up Decision at Evaluation of Patient

13.1 Patients who are responding

Patients who are sCR, CR, VGPR, PR, MR, or SD (or usCR, uCR, uVGPR, uPR, uMR) will continue treatment per protocol. Treatment may continue until disease progression as long as the patient continues to respond and does not have any unacceptable toxicity.

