13.3 Criteria for Initiation of Event Monitoring

Patients who go off protocol treatment for the following reasons will go to the event-monitoring phase per Section 4.2:

- Progressive multiple myeloma at any time on the clinical trial
- Patient requests to discontinue study treatment
- Patient develops an intercurrent illness that precludes further participation, or requires a prohibited concomitant treatment
- The Investigator withdraws the patient in the patient's best interests
- Administrative reasons (e.g., the patient is transferred to hospice care)
- An adverse event, which in the opinion of the Investigator, precludes further trial participation
- A dose omission of more than 28 days beyond the scheduled date of retreatment for daratumumab or lenalidomide

All attempts should be made to complete the End of Study procedures if a patient goes off treatment early.

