## 16.0 Statistical Considerations and Methodology

### 16.1 Overview

This is a phase II study of Daratumumab for transplant eligible multiple myeloma patients. This study is designed to assess the rate of minimal residual disease (MRD) negativity using a one stage phase II study design with an interim analysis in patients with transplant eligible multiple myeloma.

- 16.11 Primary Endpoint: The primary endpoint of this study is the rate of MRD negative response after ASCT. MRD negative response after ASCT is defined as achievement of MRD negative status in the bone marrow by flow cytometry (MPF) at the day 100 post ASCT visit. All patients meeting the eligibility criteria, who have signed a consent form and have begun treatment will be evaluable for response, unless they are determined to be a major violation.
- 16.12 Sample Size: The one stage study design with an interim analysis to be used is fully described below. A minimum of 20 and a maximum of 45 evaluable patients will be accrued total onto this phase II study unless undue toxicity is encountered. We anticipate accruing an additional 5 patients to account for ineligibility, cancellation, major treatment violation, or other reasons for a total of 50 patients overall.
- 16.13 Accrual Rate and Study Duration: The anticipated accrual rate is 2 evaluable multiple myeloma patients per month. Therefore, the accrual period for this phase II study is expected to be about 2 years. The maximum total study duration is expected to be approximately 5 years, or until the last patient accrued has been observed at least for 3 years after registration.

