#### 16.42 Secondary Outcome Analyses

The rate of MRD negative response after pre-SCT consolidation with Daratumumab will be estimated by the number of patients who achieve MRD negative status by flow cytometry (MPF) in the bone marrow after pre-SCT consolidation with Daratumumab divided by the total number of evaluable patients. Exact binomial 95% confidence intervals for the true rate of MRD negative response after pre-SCT consolidation with Daratumumab will be calculated.

The rate of MRD negative response after 1 year (12 cycles) of Daratumumab and lenalidomide maintenance will be estimated by the number of patients who achieve MRD negative status by flow cytometry (MPF) in the bone marrow after 1 year of maintenance therapy divided by the total number of evaluable patients. Exact binomial 95% confidence intervals for the true rate of MRD negative response after 1 year of maintenance will be calculated.

Progression-free survival time is defined as the time from registration to the time of progression or death due to any cause. Patients who are alive and progression-free will be censored on the date of their last disease assessment. Patients who receive subsequent treatment for myeloma before disease progression will be censored on the date of their last disease assessment prior to initiation of the subsequent treatment. The distribution of progression-free survival will be estimated using the method of Kaplan-Meier.

Survival time is defined as the time from registration to death due to any cause. The distribution of survival time will be estimated using the method of Kaplan-Meier.

The overall response rate at day 100 post ASCT will be estimated by the number of patients with an objective status of sCR, CR, VGPR, or PR at the day 100 post ASCT assessment divided by the total number of evaluable patients. Response assessment will be in comparison to values obtained at the disease assessment at the time registration. Exact binomial 95% confidence intervals for the true overall response rate at day 100 post ASCT will be calculated.

**Adverse Events:** All eligible patients that have initiated treatment will be considered evaluable for assessing adverse event rate(s). The maximum grade for each type of adverse event will be recorded for each patient, and frequency tables will be reviewed to determine patterns. Additionally, the relationship of the adverse event(s) to the study treatment will be taken into consideration.

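### Read literally, the 3-year stop covers only patients in event monitoring, so the Kaplan-Meier overall survival curve beyond month 36 is biased upward; the plan sets no survival horizon to prevent this

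*Combined protocol and SAP*

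**What the plan says.** Section 4.2 sets the contact schedule for the event monitoring phase. Footnote 1, attached to that phase's column heading, reads: "If a patient is still alive 3 years after registration, no further follow-up is required". Section 13.3 lists what moves a patient into the phase. All the listed reasons are reasons for leaving protocol treatment, and one of them is "Progressive multiple myeloma at any time on the clinical trial".

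Patients who have not left treatment follow a different schedule. From Cycle 16 (or 18), section 7.13 provides "maintenance with single-agent daratumumab every 3 months till disease progression or unwanted adverse events, if any". Section 13.1 adds: "Treatment may continue until disease progression as long as the patient continues to respond and does not have any unacceptable toxicity". Neither section sets a calendar limit, and the test schedule in 4.1 continues at the end of each cycle.

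Section 16.13 expects about 2 years of accrual and about 5 years in total, or "until the last patient accrued has been observed at least for 3 years after registration". Section 16.42 defines OS from registration to death from any cause and says: "The distribution of survival time will be estimated using the method of Kaplan-Meier". It gives censoring rules for progression-free survival (PFS) but none for OS, and no horizon for either.

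**The concern.** Kaplan-Meier needs the patients who leave the risk set to have the same outlook as those who stay. The literal reading breaks this after month 36. Patients already in event monitoring may be dropped at month 36. Patients still on treatment continue to be observed, but on progressing they enter a phase in which nothing further is required of them. Leaving observation is then tied to progression, which is when the risk of death rises.

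OS is secondary objective 2.26, and section 16.6 commits to public reporting of the secondary endpoints. A flattening of the curve after year 3 could be read as durable benefit when the follow-up rule produced it. In a single-arm trial there is no control curve subject to the same rule to reveal this.

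**Working it through.** **The plan's own figure.** Study duration is accrual plus 36 months. At 2 patients per month, 45/2 + 36 = 58.5 months and 50/2 + 36 = 61 months. This agrees with the stated 5 years or so. Potential follow-up therefore runs from 36 months (last patient) to about 61 months (first patient).

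**Can patients still be on treatment at month 36?** With every window at its longest, Cycle 16 starts after 28 + 84 + 124 + 12 × 28 = 572 days, and Cycle 18 after 3 × 28 + 84 + 124 + 12 × 28 = 628 days. At 30.4375 days per month that is 18.8 and 20.6 months. Open-ended daratumumab is thus well under way before month 36.

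**Inputs for the size of the bias.** Section 1.4 gives one anchor: "The majority of post-ASCT patients relapse with median PFS around 36 months". The rest is assumed, because the documents give no figure:
- PFS exponential, median 36 to 50 months from registration;
- post-progression survival exponential, median 24 to 36 months;
- q = 5% of PFS events are deaths without progression;
- 45 patients, 25 months of uniform accrual, data cut at month 61;
- footnote applied strictly.

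**Formulas.** Let λ = ln 2 / (median PFS) and μ = ln 2 / (median post-progression survival).
- True OS: S(t) = exp(−λt) + (1 − q) × λ/(μ − λ) × [exp(−λt) − exp(−μt)]. When μ = λ, it is exp(−λt) × [1 + (1 − q)λt].
- Literal reading: after month 36 only deaths without progression are seen in the risk set, at rate qλ. The estimate at 48 months tends to S(36) × exp(−qλ × 12).

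**Worked case (36 and 24 months).** λ = 0.01925, μ = 0.02888 and λ/(μ − λ) = 2.
- S(36) = 0.5 + 0.95 × 2 × (0.5 − 0.3536) = 77.8%.
- S(48) = 0.3969 + 0.95 × 2 × (0.3969 − 0.25) = 67.6%.
- Estimate at 48 months = 77.8% × exp(−0.05 × 0.01925 × 12) = 76.9%.
- Excess = 9.3 points. Up to month 36 it is zero, since everyone is followed to that point.

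| Median PFS | Median post-progression survival | True OS, 48 months | Estimate, 48 months | Excess (points) |
|---|---|---|---|---|
| 36 | 24 | 67.6% | 76.9% | 9.3 |
| 36 | 36 | 74.5% | 82.0% | 7.4 |
| 50 | 24 | 74.6% | 82.3% | 7.7 |
| 50 | 36 | 80.0% | 86.2% | 6.1 |

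**Sensitivity.** A simulation of the worked case that follows each patient one month past progression, to approximate the 30-day death reports, gives 76.5% instead of 76.9%. A wider grid (median PFS 24 to 48, post-progression 12 to 36 months, q = 10%) gives about 6 to 12 points.

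**How many patients support the curve there.** Entry must fall in the first 61 − 48 = 13 of 25 months, without progression by month 48:
- median PFS 36: 45 × 13/25 × 2^(−48/36) = 9.3;
- median PFS 50: 45 × 13/25 × 2^(−48/50) = 12.0.

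At 59 months the same sum is 45 × 2/25 × 2^(−59/36) = 1.2, or 1.6 with median 50. These counts ignore stopping treatment for other reasons, so they are upper figures.

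**The case against.** The strongest reply is that the footnote can be read as a limit for everyone. It speaks of a patient without qualification, the section title includes survival follow-up, and 16.13 uses the same 3 years. Under that reading all patients stop at month 36 and the bias does not arise. This stands, and it makes the point conditional. It does not settle it: the footnote hangs on the event monitoring phase, while 7.13 and 13.1 keep patients on treatment with no such limit. The plan does not say which reading applies.

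The other reply is that OS is secondary and descriptive, and that a fixed 3-year horizon is a legitimate choice in a phase II trial built on day-100 MRD. That is correct. The gap is that 16.42 does not state such a horizon.

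A reader might also infer stronger claims that the documents do not support:
- *That no post-progression death after month 36 can be counted.* Follow-up is only not required, so recording a later death is not barred. Deaths within 30 days of the last dose remain reportable whatever the cause, and later ones if judged at least possibly treatment-related (4.1 note h, 10.52, 10.62). The accurate statement is that almost none are captured.
- *That the OS curve as a whole is biased.* It is unbiased to month 36 under either reading.
- *That PFS suffers as well.* The two harms belong mainly to different readings. If everyone stops at month 36, PFS ends there: with a 36-month median, 45 × 0.5 = 22.5 events against about 27 at a common close, but with no OS bias. Under the literal reading, later progressions on treatment are still seen, and PFS loses only late events in patients who stopped treatment without progressing.
- *That the gap at 59 months is a useful figure.* It rests on 1 to 2 patients, and the plan sets no such landmark.

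**Conclusion.** The point holds in conditional form. Applied as written, the follow-up rules leave an OS risk set after month 36 made up of patients on treatment without progression, who leave it at progression, so the Kaplan-Meier curve is too high from there on. The excess at 48 months is about 6 to 9 points, given exponential times, median PFS of 36 to 50 months, post-progression medians of 24 to 36 months and strict use of the footnote, with roughly 9 to 12 of 45 patients at risk. Only the 36-month PFS figure has a source in the protocol. It describes patients after transplant, whereas this trial counts from registration, so the sizes are illustrations. The direction does not depend on them, provided progression raises the risk of death. Later landmarks should not be quoted. The primary MRD decision rule, its significance level and its power are untouched. The correction is worth making because it is nearly free and protects a stated objective.

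**What to change.** 1. In 16.42, state that OS is censored at 36 months from registration for all patients, including those still on treatment, and is reported only to that point. If footnote 1 is meant to cover everyone, give PFS the same horizon.
2. In 4.2, state whether footnote 1 applies to patients still on treatment.

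The cost is about one sentence in each section. The downside is that OS information after month 36 is not used.

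Optional alternative, at the sponsor's choice: follow every patient for survival to the common close-out already in 16.13. That keeps the later information and also removes the bias. The first patients would be followed for up to 61 − 36 = 25 further months. At the 4.2 intervals this is up to about 25/6 ≈ 4 contacts per patient after progression or subsequent therapy, and up to about 25/3 ≈ 8 for patients off treatment without progression. Neither route changes treatment, sample size or the primary analysis.
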